1. STUDY SYNOPSIS AND OBJECTIVES

1.1 STUDY SYNOPSIS

STUDY TITLE	Aneurysmal Subarachnoid hemorrhage Trial RandOmizing Heparin (ASTROH)
PRIMARY OBJECTIVES	The primary objective of this study is to investigate the safety and clinical effect of a continuous low-dose intravenous unfractionated heparin (LDIVH) infusion for the prevention of aneurysmal subarachnoid hemorrhage (aSAH) induced neurocognitive dysfunction. The rate of “Major Bleeding” or “Clinically Relevant Non-Major Bleeding” as defined by the International Society of Thrombosis and Haemostasis (ISTH) between the LDIVH and the control group will be compared. The mean Montreal Cognitive Assessment (MoCA) scores obtained at a 90-day follow-up visit will be compared between LDIVH treated patients and controls. We expect the results of this study to inform on whether a properly powered Phase III study evaluating a LDIVH infusion for aSAH is warranted.
SECONDARY OBJECTIVES	Increased blood and CSF levels of certain inflammatory biomarkers have been correlated to aSAH patients with poor clinical outcomes. Unfractionated heparin (UFH) has known anti-inflammatory actions. As a result, a secondary objective of this study will be to evaluate whether LDIVH can reduce blood and CSF inflammatory biomarker levels compared to controls and whether there is any association between inflammatory biomarker levels and cognitive outcomes in aSAH.
STUDY DESIGN	Investigator initiated and sponsored, multicenter, prospective, 1:1 randomized, open-label, blinded adjudication phase II study. Study patients randomized to the LDIVH arm will receive normal standard of care (SOC) plus a continuous low-dose intravenous infusion of UFH for up to 14 days. During the 14-day infusion, the LDIVH arm study subjects will not receive any chemical deep venous thrombosis

	
(DVT) prophylaxis but may resume chemical DVT prophylaxis after the 14-day infusion is complete. Study patients randomized to the control arm will receive the normal standard of care (SOC), which will be UFH 5,000 units, twice daily.

STUDY POPULATION	
Patients with a supratentorial aSAH secondary to a ruptured cerebral aneurysm that has been secured by endovascular coil embolization. Study subjects must score as a WFNS SAH grade ≤ 2 post-coiling with no significant aphasia at the time of enrollment and have a significant hemorrhage burden on the initial head computed tomographic (CT) scan that demonstrates a modified-Fisher grade 3, or grade 4 (with minimal intraparenchymal blood or IVH less than 25%.)

CLINICAL SITES	
Eight to ten designated clinical sites in the USA.

PLANNED ENROLLMENT	
88 patients (44 in each treatment allocation group; Approximately 5-6 patients per site per year average)

STUDY DURATION	
3 years [2 years enrollment; 3 months primary end-point follow-up visit; 3 months data analysis and reporting of results; 1-year follow-up visit secondary endpoint].

PRIMARY SAFETY ENDPOINT	
Rate of “Major Bleeding” or “Clinically Relevant Non-Major Bleeding” as defined by the International Society of Thrombosis and Haemostasis (ISTH) between the groups from enrollment until discharge from the acute inpatient setting.

SECONDARY SAFETY ENDPOINT	
Rate of Symptomatic Intracranial Hemorrhage between the two groups from enrollment until discharge from the acute inpatient setting. A symptomatic hemorrhage is defined as a 4-point or greater increase in the NIHSS or a decrease in the GCS by 2 or more points not explained by other causes.

ADDITIONAL PRESPECIFIED SAFETY OUTCOMES TO BE ANALYZED	
Rate of any new intracranial hemorrhage between the two groups from enrollment until discharge from the acute inpatient setting.
 
Rate of Serious Adverse Events (SAEs) between the two groups from enrollment until

the 90-day follow-up visit as reported by each site and adjudicated by an independent Clinical Events Adjudication Committee (CEC).

Rate of Type II Heparin Induced Thrombocytopenia (HIT) between the two groups from enrollment until the 90-day follow-up visit

Rate of DVT or PE between the two groups from enrollment until the 90-day follow-up visit

All cause and neurological mortality rates between the two groups from enrollment until the 90-day follow-up visit

PRIMARY CLINICAL EFFECT ENDPOINT

Mean Montreal Cognitive Assessment score (MoCA) at 90 (± 10) days post enrollment.

SECONDARY ENDPOINTS:

-PRIMARY BIOMARKER ENDPOINT

Peak and Overall Plasma and CSF levels of hsCRP at enrollment and, infusion days #2, 4, 6, and 10 compared between groups.

-SECONDARY CLINICAL EFFECT ENDPOINTS

Trail Making Test Parts A&B at 90 (± 10) days post enrollment.

MoCA at 1-year (± 30 days)

Center for Epidemiologic Studies Depression Scale (CES-D) at 90 (± 10) days post enrollment

Return to work status between groups at 90 (± 10) days

SECONDARY EXPLORATORY PRESPECIFIED BIOMARKER OUTCOMES

Plasma and CSF levels of IL-6, TNF- α , P-Selectin, sICAM-1, HMGB-1, MRP8/14 plasma levels at enrollment and infusion day #2, 4, 6, and 10

ADDITIONAL PRE-SPECIFIED

Rate of MoCA ≤ 20 between groups at the 90-day follow-up visit.

**EXPLORATORY
OUTCOME ANALYSES**

In-hospital incidence of any fever ($> 38.3^{\circ} \text{C}$; $\geq 101.0^{\circ} \text{F}$), Incidence of multiple fever episodes (≥ 3), and Mean Daily Fever Burden.

GCS and NIHSS at enrollment and infusion days # 2,4,6,10, discharge and 90 (± 10) days

MoCA at post-enrollment day #1, 6 and 10

Correlation analysis between MoCA scores and inflammatory biomarker levels with and without adjusting for hemorrhage burden (Hijdra Sum Score).

Incidence of moderate and severe Radiographic Cerebral Vasospasm based on a CTA, MRA, or Catheter DSA obtained between PBD # 6-12 as determined by an independent and blinded core imaging lab.

Incidence of TCD criteria for significant vasospasm (velocities $>200 \text{ cm/s}$ and / or MCA / ICA (Lindgaard) ratio >6)

Incidence of TCD criteria for absence of vasospasm (velocities $<120 \text{ cm/s}$)

Incidence of clinical vasospasm requiring rescue therapy (eg, pressors, endovascular treatment)

Incidence of "Delayed Cerebral Ischemia" defined as:

- Symptoms of neurological deterioration (e.g. hemiparesis, aphasia, decreased level of consciousness)
- Symptoms last for more than an hour
- Symptoms are not explained by other physiological processes (e.g., hydrocephalus, hypotension)

CT or MRI evidence of Vasospasm Related Cerebral Infarction on post-infusion (discharge) imaging as scored by an independent and blinded core imaging lab

Global outcome as measured between group ordinal regression analysis of the modified Rankin Scale score at 90-days and 1-year.
Return to work status between groups at 1-year.
Lawton IADLs at 90 (± 10) days
QOLIBRI-OS at 90 (± 10) days and 1-year.
Checklist Individual Strength-subscale Fatigue (CIS-f) at 90 (± 10) days
Barthel Index at 90 (± 10) days and 1-year

**INVESTIGATIONAL
STUDY DRUG NAME
AND FORMULATION**

Unfractionated Heparin (UFH) intravenous solution at a concentration of 100 units per ml (25,000 to 50,000 units of heparin in 250 to 500 ml of 0.9% or 0.45% NaCl solution)

INTENDED USE

A prophylactic infusion of LDIVH for up to 14 days with prescribed escalated dosing until the goal aPTT value is achieved. The LDIVH infusion is intended to prevent cognitive deficits in modified-Fisher grade 3 and 4 aneurysmal subarachnoid hemorrhage survivors following endovascular coil embolization of the ruptured cerebral aneurysm. The LDIVH infusion is to be initiated 12 ± 4 hours after coiling of the aneurysm. The infusion will be started at 8 units/kg/hr (0.08 cc/kg/hr) and increased by 2 units/kg/hr every 12 hours until the goal aPTT is reached (typically 12 u/kg/hr) *Note: The goal aPTT is an institution specific aPTT value that correlates with an anti-Xa assay value of 0.1 – 0.3 IU/ml of heparin.*

STUDY SUCCESS

For the purposes of this trial, study success is defined as demonstrating a statistically significant improvement in the mean MoCA score for the LDIVH arm compared to the control arm of the study at the 90-day follow-up visit or a significant reduction in inflammatory biomarker levels in the LDIVH arm compared to the control arm. In addition, there can be no significant differences between groups in the rate of Major Bleeding or Clinically Relevant Non-Major Bleeding attributable to the LDIVH treatment.

PATIENT COMPLETION

Patient completion in the study occurs when the patient has completed his/her 1-year follow-up

visit and all case report forms (CRFs) and Imaging required by the Study Protocol have been completed OR the patient has withdrawn from the study or has been determined to be “Lost to Follow-up” and all available CRFs and Imaging have been collected and submitted to the University of Louisville. The primary endpoint is the 90-day follow-up visit and therefore the primary data-analysis will occur after this date.

**PRIMARY PRINCIPAL
INVESTIGATOR (PPI) /
SPONSOR**

[name]
Associate Professor of Neurosurgery
Chief, Vascular Neurosurgery
University of Louisville School of Medicine
Louisville, KY
[contact];
[contact]

**CO-PRINCIPAL
INVESTIGATORS (Co-PI)**

J. [name], PhD
Professor of Neurosurgery, Pathology & Physiology
University of Maryland Medical Center
Baltimore, MD

[name]
Professor and Vice Chair for Education
Department of Neurosurgery
Director, Cerebrovascular Surgery Program

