6.6 Collection Of Baseline Patient Information

[May occur prior to enrollment, during screening process and may be completed after enrollment for those items not related to eligibility]

During screening, after informed consent has been obtained, or following enrollment baseline information may be collected.

The CRFs for this trial were developed as modifications of the stroke modules provided by the NIH/NINDS common data elements (CDEs) for clinical trials program.

Clinical and historical assessments will include: historical pre-morbid mRS, Assessment for Dementia and pre-morbid employment status. Assessments of NIHSS and MoCA, having occurred immediately prior to enrollment or soon after enrollment.

Baseline biomarker specimens will be obtained after enrollment but prior to initiation of study drug or within 6 hours of initiating study drug.

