6.7 Baseline Blood And Biomarker Specimen Collection

Please draw all normal blood tests as you would for your normal standard of care for the treatment of an aneurysmal subarachnoid hemorrhage. hsCRP and Anti-Xa levels will be drawn for all subjects after enrollment but prior to initiation of the study drug (for those subjects in the LDIVH treatment group).

Additional blood will be drawn and processed to plasma and stored for additional biomarker analysis. This may be performed up to 6 hours after initiation of study drug for the LDIVH arm (but preferably prior to study drug initiation). Please see the section below on the collection and processing of plasma biomarker specimens Section 6.11

If the subject already has an external ventricular drain or a lumbar drain placed, then removal of cerebrospinal fluid should be performed again with processing of the specimens for biomarker analysis. This may be performed up to 6 hours after initiation of study drug for LDIVH arm (but preferably prior to study drug initiation). Please see the section below on the collection and processing of CSF biomarker specimens Section 6.11.

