In addition, the T_{max} per 24-hour period will be documented in the study CRF/Database as well as the number of temperature values recorded as a fever ($>38.3^{\circ}\text{C}$) per 24 hour period. **For the purposes of this study, a day will run from 7 AM until 6:59 AM the following morning.**

Daily T_{max} , Daily Fever Burden, and # of fevers per day will be evaluated as an outcome measure on enrollment day # 2, 4, 6, and 10 to determine any correlation between fever and individual inflammatory biomarker levels and neurological assessments and MoCA scoring at each time point (# 6 and 10). Also, the mean of each subject's average hospitalization daily fever burden (up to 21 days) will be analyzed in relation to the mean of the biomarker levels summed over enrollment days #2, 4, 6, and 10 per study treatment group. Finally, presence of any temperature $> 38.3^{\circ}\text{C}$ and multiple febrile episodes (>2) for a study subjects will be noted and compared between treatment groups as an analysis of categorical proportions.

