10.4 General Statistical Plan

Patients enrolled will be presented. On-study protocol violations will also be presented. Patients who do not complete the required observations will be listed and evaluated separately as necessary. Reasons for study discontinuation and date of withdrawal from study will be presented.

Descriptive statistics related to the participant characteristics, treatment, and prognostic factors will be reported. For the continuous variables mean (95% confidence interval), median (minimum and maximum) will be reported and for discrete variables frequency and percentages will be reported. For continuous variables a two sample t-test/rank sum test will be used to compare between groups. A Chi-square test will be used for establishing association between categorical variables. For example MoCA will be compared between two groups using a contrast based t test in addition to simple two sample test either based on a linear regression or Mixed model approach when multiple observations on sample subject is considered. A discrete outcome such as prevalence of 'have any fever' between treatment and control arms will be tested using a logistic regression analyses. In order to examine the significant prognostic factors, we will use the multiple linear and logistic regression models in multi-variable setting.

A significance level of 5% will be used to declare results significant. For selected primary outcome variables we will report adjusted p-values for multiplicity in addition to unadjusted p-values. All calculations will be performed with methods described in Walker et al. (2010), Rosner (2010) and with SAS statistical software (SAS, 2003).

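### The primary biomarker endpoint counts the pre-treatment enrollment hsCRP in its peak and overall levels, with no baseline adjustment stated, which dilutes the heparin contrast and costs power

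*Protocol*

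**What the plan says.** The synopsis (section 1.1) gives the primary biomarker endpoint as "Peak and Overall Plasma and CSF levels of hsCRP at enrollment and, infusion days #2, 4, 6, and 10 compared between groups". It does not say whether overall is a mean, a sum, an area under the curve or a model estimate.

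On timing, section 6.7 states: "hsCRP and Anti-Xa levels will be drawn for all subjects after enrollment but prior to initiation of the study drug". Section 6.6 is looser for baseline biomarker specimens in general: "Baseline biomarker specimens will be obtained after enrollment but prior to initiation of study drug or within 6 hours of initiating study drug". Sections 6.7 and 6.11 tie CSF collection to the presence of a drain, and 6.7 lets the baseline CSF be taken up to 6 hours after the infusion starts.

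On analysis, section 10.4 gives a default: "For continuous variables a two sample t-test/rank sum test will be used to compare between groups". With MoCA as its example, it then allows a comparison "either based on a linear regression or Mixed model approach when multiple observations on sample subject is considered". It names no baseline term for hsCRP and excludes none.

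Two other places treat the enrollment value differently. Section 6.12.6 uses "the mean of the biomarker levels summed over enrollment days #2, 4, 6, and 10 per study treatment group" in its fever analysis, leaving enrollment out. Section 1.2.2, item 10, uses enrollment hsCRP as a baseline subgroup factor.

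The synopsis definition of study success asks for better MoCA "or a significant reduction in inflammatory biomarker levels in the LDIVH arm compared to the control arm", together with no significant bleeding difference.

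**The concern.** The question is whether heparin lowers hsCRP. A blood value taken before heparin starts cannot answer it. Placed inside the outcome, that value pulls any average toward no difference. It also supplies a pre-treatment number as the peak for every subject whose highest reading is at enrollment. The same value is more useful as a covariate, where it removes between-subject variation from the comparison.

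Because a biomarker reduction can carry the trial's conclusion without MoCA, power lost here could turn a real effect into a failed criterion, and the reported difference would be understated.

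**Working it through.** **What the plan gives.** There is no sample size, SD, effect or correlation for hsCRP, so there is no hsCRP figure to reproduce. The 40 evaluable subjects per arm come from section 10.1 and were set for MoCA. That figure reproduces: with SDs 7.0 and 2.5, a difference of 3 and one-sided 5%, the unequal-variance t-test needs 40 per arm (power 80.8%).

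**Assumptions.** SD 1 at each of the five times, a common correlation ρ between any two times, the same effect d at days 2, 4, 6 and 10, no effect at enrollment, and overall taken as an equally weighted mean. None of these comes from the protocol.

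**Step 1: dilution of the overall mean.** The difference in the five-point mean is (0 + 4d)/5 = 0.8d, which is 20% too small at any ρ.

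**Step 2: information, as effect² / variance (d = 1).**
- Five-point mean: 0.64 / [(1 + 4ρ)/5]
- Four-point mean, days 2–10, unadjusted: 1 / [(1 + 3ρ)/4]
- Four-point mean adjusted for enrollment: 1 / [(1 + 3ρ)/4 − ρ²]

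Since (1 + 3ρ)/4 − ρ² = (1 − ρ)(1 + 4ρ)/4, the information in the five-point mean relative to the others is:
- against dropping enrollment only: 0.8(1 + 3ρ)/(1 + 4ρ)
- against dropping and adjusting: 0.8(1 − ρ)

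| ρ | Loss vs dropping | Loss vs dropping and adjusting |
|---|---|---|
| 0 | 20% | 20% |
| 0.3 | 31% | 44% |
| 0.5 | 33% | 60% |
| 0.7 | 35% | 76% |

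The first loss never exceeds 36% (ρ = 1: 0.8 × 4/5 = 0.64). The second exceeds one half only when 0.8(1 − ρ) < 0.5, that is ρ > 0.375.

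**Step 3: illustrative power.** Power = Φ(0.5 × √information × √(40/2) − z), for an assumed effect of 0.5 SD and 40 per arm. Section 10.1 adopts one-sided testing for MoCA; sidedness for hsCRP is not stated, so both are shown.

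| ρ | Five-point mean, one-sided (two-sided) | Dropped only | Dropped and adjusted |
|---|---|---|---|
| 0.3 | 85% (77%) | 95% (90%) | 97% (95%) |
| 0.5 | 75% (64%) | 88% (81%) | 98% (95%) |
| 0.7 | 66% (54%) | 82% (72%) | 99% (99%) |

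**Step 4: sensitivity to the common correlation.** Let enrollment correlate r0 with later values, and later values r1 with each other. At r0 = 0.3 the two losses are 25% and 36% with r1 = 0.5, and about 22% and 31% with r1 = 0.7. The second loss passes one half at r0 = 0.42 (r1 = 0.5) or 0.48 (r1 = 0.7).

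**Step 5: peak.** Simulation with normal values, 400,000 per arm and a true effect of 0.50 SD:

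| Rise after enrollment | Peak difference, enrollment included (ρ 0.3 to 0.7) | Dilution |
|---|---|---|
| 0 | 0.34–0.36 | about 30% |
| 0.5 SD | 0.43–0.44 | about 12–14% |
| 1 SD | 0.47–0.49 | about 3–6% |
| 1.5 SD | 0.49–0.50 | 2% or less |
| 2 SD | 0.50 | under 1% |

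**The case against.** The strongest case on the other side has five parts.

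- **The synopsis line may only list sampling times.** GCS and NIHSS are listed there in the same form, as a schedule. This is a possible reading, but then peak and overall have no stated window, and the same rewording is needed.
- **Adjustment is unstated, not rejected.** A reader might infer that the plan has decided against using enrollment hsCRP as a covariate. The text does not support that: section 10.4 allows regression and mixed models, and an analysis plan that is not shown may fix the covariates. A longitudinal model can also keep enrollment in the outcome vector under a common baseline mean. Even so, adjusting a five-point mean for enrollment would restore the test but leave the estimate at 0.8d, and peak would still contain pre-treatment maxima.
- **Peak may hardly be affected.** Section 5.2 expects the inflammatory response to peak after treatment starts. If hsCRP follows that course, step 5 shows little dilution. This stands.
- **CSF differs from blood.** CSF is not collected in everyone, and its baseline sample may follow up to 6 hours of infusion. The 40-per-arm power figures do not carry over to CSF. This stands.
- **Section 6.12.6 is a separate fever analysis.** It does not contradict the endpoint. It shows only that the protocol already uses a post-enrollment summary.

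**Conclusion.** The point holds for the endpoint as worded: a pre-treatment blood value sits inside the summaries being compared, and no baseline adjustment is stated. For an equally weighted overall mean the difference is 20% too small whatever the correlation. The loss of information depends on assumed correlations: about 31% to 35% from including enrollment, and 44% to 76% against the adjusted analysis, for a common ρ of 0.3 to 0.7. Part of the second range comes from the missing covariate and not from the inclusion itself. Peak is affected only to the extent that hsCRP fails to rise after enrollment.

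Two stronger readings are tempting and should not be drawn. One is that the endpoint throws away most of its precision. That needs a correlation above about 0.38 (0.42 to 0.48 with separate correlations), and the protocol gives none. The other is that the wording could produce a false success. Dilution is conservative, and a chance imbalance in enrollment hsCRP is random error already covered by the test's significance level. The cost is lost power and an understated difference, on a criterion that can decide study success.

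**What to change.** Reword the endpoint: peak and overall (time-averaged) hsCRP over days 2, 4, 6 and 10, compared between groups with enrollment hsCRP as a covariate. An equivalent choice is a mixed model with all five times and a common baseline mean in the two arms, with the treatment contrast taken over days 2 to 10.

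For CSF, use the post-enrollment summary and adjust only where a baseline sample exists, or use the common-baseline mixed model, which keeps subjects whose drain was placed later.

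The change is to endpoint and analysis wording and needs no additional samples. Its one cost is a stated rule for missing enrollment values, which will arise mainly in CSF.

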6.11 Inflammatory Biomarker Collection and Processing

hs-CRP blood levels will be drawn and processed by each site's clinical laboratory and the results of these tests will be documented in the database CRFs for each time point which will include time of enrollment, and post-enrollment days #2, 4, 6, and 10. As such, these values will be immediately available to the DSMB and Steering Committee during the interim analysis.

hs-CRP levels will be measured in the CSF as well. CSF will be sent to the local institution's lab for analysis of hs-CRP in the appropriate tube per the lab's standard procedure.

Additional blood and CSF (when a drain is present) will be drawn at enrollment and post-enrollment days # 2, 4, 6 and 10. The blood and CSF will be processed and stored locally and then shipped to the biomarker core lab for further planned biomarker analysis to be processed in a batch fashion after all samples have been collected. Currently the planned biomarkers to be analyzed include: IL-6, TNF- α , P-Selectin, ICAM-1, HMGB-1, and MRP 8/14.

Biomarker processing kits will be mailed to each site that will include instructions, transfer pipettes, shipping packaging, specimen box, pre-filled labels, and other supplies necessary to process blood to plasma and store them in the -70°C freezer. Each site will need to supply venipuncture supplies (needles, vacutainer tubes, or butterfly needles). Each site will also need to supply their own centrifuge, ice bucket, dry ice, and -70°C freezer space.

Collection of Biomarker Blood Specimens and Processing to Plasma:

1. **Collect 9-10 ml of venous blood** using a lavender top Vacutainer (EDTA). Mix according to standard guidelines. If collecting blood from an IV, PICC, or other line, make sure there are no medications hooked up to the line (such as heparin), if there are, temporarily turn off these infusions and waste at least 5 cc of blood prior to collecting the specimen. Turn infusions back on at the same rate following the blood draw.
2. **Within 30 minutes of the blood draw, centrifuge the tube for 10 min at 500g** (approx. 2,000 rpm in a standard centrifuge). If samples cannot be processed within 30 minutes, the tubes should be kept on ice until they can be centrifuged (*no more than 2 hours delay*). **Do NOT freeze the whole blood samples!** Heavily hemolysed or lipemic samples are to be avoided.

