8.6 DATA SAFETY MONITORING BOARD (DSMB)

A Data Safety Monitoring Board (DSMB) charter will be created that will specify all of the rights and duties of the DSMB. The DSMB Chair and the PPI will draft the DSMB charter with input from the biostatistician. This protocol is not meant to supersede that document and the terms of that document will take priority over any conflicting terms or statements listed within this study protocol.

The DSMB will meet (in person or virtually) periodically (at least annually) to review the progress of this study (e.g enrollment, site performance, data quality, meeting risk factor targets) as well as data on the safety of both treatment arms (e.g. complications of LDIVH infusion). Before the study begins, the DSMB will decide on the frequency and timing of interim safety analyses. The DSMB may recommend termination of the study if the LDIVH treatment arm is found to be unsafe. The DSMB may also recommend protocol revisions to address enrollment, safety, etc. There will be no interim analysis of efficacy by the DSMB. The DSMB may also recommend modifications to the protocol if reversible safety issues are identified. The primary principal investigator ([name]) may attend the DSMB meetings as a resource to the DSMB, but will not be allowed to vote and may be dismissed from the meeting(s) at anytime by the DSMB chair. The primary principal investigator will always be dismissed if there is any discussion of unblinded outcome measures. After each meeting, the DSMB Chair will prepare a letter to the study's primary principal investigator ([name]), Steering Committee, and site investigators, which will document the safety review that took place at the meeting. This letter will indicate whether or not there are any safety concerns. This letter will be provided to any of the IRBs at participating sites at their request. Safety of study participants is of the utmost importance.

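### Success may be claimed on MoCA or on an unspecified biomarker reduction, with no error control tied to that choice, so the false-success rate exceeds 5%

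*Protocol*

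**What the plan says.** Protocol section 1.1 (Study Success): "study success is defined as demonstrating a statistically significant improvement in the mean MoCA score for the LDIVH arm" over control at 90 days, "or a significant reduction in inflammatory biomarker levels in the LDIVH arm compared to the control arm". A safety condition is added: "there can be no significant differences between groups in the rate of Major Bleeding or Clinically Relevant Non-Major Bleeding" attributable to the infusion.

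The same synopsis places hsCRP under secondary endpoints, as the primary biomarker endpoint: "Peak and Overall Plasma and CSF levels of hsCRP at enrollment and, infusion days #2, 4, 6, and 10 compared between groups". That is peak and overall, in plasma and in CSF. Six further markers (IL-6, TNF-alpha, P-Selectin, sICAM-1, HMGB-1, MRP8/14) are listed as exploratory.

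The efficacy part of the primary objective (section 1.2.1) is MoCA alone, and section 10.1 builds the sample size on MoCA with a one-sided 5% test.

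Section 10.4: "A significance level of 5% will be used to declare results significant". On multiplicity: "For selected primary outcome variables we will report adjusted p-values for multiplicity in addition to unadjusted p-values".

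On interim access to hsCRP, section 6.11 says that "these values will be immediately available to the DSMB and Steering Committee during the interim analysis", while section 8.6 says "There will be no interim analysis of efficacy by the DSMB".

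**The concern.** The efficacy part of the rule is an OR between the primary clinical endpoint and something that ranks as secondary everywhere else in the protocol. Each side of the OR is a separate chance of a positive result at the nominal level, and the biomarker side is not pinned to one comparison. The multiplicity sentence in section 10.4 covers unspecified primary variables, reports adjusted p-values next to unadjusted ones, and does not say which of the two decides success. Biomarkers are not primary variables, so the sentence does not reach them.

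The trial is meant to inform whether a Phase III study is warranted. As written, that case could rest on a declared success with no MoCA benefit, at an error rate the protocol neither states nor limits.

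**Working it through.** **Inputs.** From section 10.1: MoCA difference 3, SD 7.0 (control) and 2.5 (treatment), one-sided alpha 5%, 40 evaluable per arm. From section 1.1: four hsCRP comparisons. From section 10.4: 5% per result, sidedness of the biomarker tests not stated. Both readings are therefore shown: 5% one-sided, or 2.5% in the reduction direction of a two-sided 5% test. The documents give no correlations between tests, so those used are assumptions.

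**The plan's own figure.** One-sided Welch t test at 40 per arm: standard error = sqrt((7.0² + 2.5²)/40) = sqrt(55.25/40) = 1.175; noncentrality = 3/1.175 = 2.55; about 48.8 degrees of freedom; power 80.8%. The same calculation gives 40, 46 and 54 per arm for 80%, 85% and 90%, matching Table S1. MoCA by itself is sized as stated, and by itself its false-positive rate is 5%.

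**False success under the OR rule, no true effect.** With m independent biomarker tests each at level a in the favourable direction, the rate is 1 − 0.95 × (1 − a)^m.

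- One test, a = 0.05: 1 − 0.95 × 0.95 = 9.8%.
- One test, a = 0.025: 1 − 0.95 × 0.975 = 7.4%.
- Four tests, a = 0.05: 1 − 0.95^5 = 22.6%.
- Four tests, a = 0.025: 1 − 0.95 × 0.975^4 = 14.2%.

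The four hsCRP tests will be correlated, so they were also simulated (400,000 multivariate normal draws, biomarker tests equicorrelated, MoCA uncorrelated with them):

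| Correlation among the four tests | a = 0.025 | a = 0.05 |
|---|---|---|
| 0 | 14.2% | 22.6% |
| 0.5 | 12.4% | 18.6% |
| 0.8 | 10.5% | 15.0% |

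Allowing a correlation of 0.3 between MoCA and the markers lowers the 0.5 and 0.8 rows by one percentage point or less (for example 15.0% to 14.2%).

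**Bleeding condition.** With equal bleeding in the arms, a significant difference would block success 2.5% to 5% of the time, so the rates are multiplied by about 0.95 to 0.975. The smallest single-test figure becomes 7.4% × 0.95 = 7.0%; the four-test figure at correlation 0.8 and a = 0.025 becomes 10.5% × 0.95 = 10.0%. All stay above 5%.

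**After repair.** MoCA as sole criterion: 5.0%, power unchanged at 80.8%. OR rule kept with one named hsCRP test and alpha split 0.025 + 0.025: at most 5.0%, but MoCA power at 40 per arm falls to 70.6%. The normal approximation then asks for 55.25 × (1.96 + 0.842)²/9 = 48.2, so 49 per arm, to regain 80%; for the plan's own case the same approximation gives 38 against the exact 40.

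**The case against.** The strongest reply is that the synopsis does contain a hierarchy. hsCRP is the named biomarker endpoint and the other markers are exploratory, so a sensible reader takes the biomarker route to mean hsCRP, perhaps a single comparison that an analysis plan would name. In an 88-patient Phase II trial, a mechanistic route to a go decision is a legitimate choice, and section 10.4 does promise some adjusted p-values.

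Much of this stands, and it bounds the point. Three stronger readings are tempting, and the documents do not support them:

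- A reader might infer that any of the biomarkers can win the trial. With seven markers in two fluids (14 independent tests at 5%) the rate would be 53.7%. The success rule does not say that exploratory markers count, although it does not rule it out, and section 1.2.2 uses similar wording with an open list of examples. Independence is also unrealistic for markers from the same patients; at correlation 0.8 the figure is 21.2%.
- A reader might infer that the protocol has no multiplicity provision at all. It has one, but it is not tied to the success decision.
- A reader might infer that Steering Committee access to hsCRP raises the type I error. Sections 8.6 and 10.5.1 provide no efficacy look and no efficacy stopping, section 6.11 does not say that values are shown by arm, and no inflation figure can be derived.

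What the reply does not rescue is the OR itself. Even one hsCRP test takes the rate above 5%, and a secondary result can replace a failed primary. That is set by the protocol's own definition and is more than detail left to an analysis plan.

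**Conclusion.** The success rule does not hold its error at 5% on any reading tried. With no true effect, MoCA at one-sided 5% and before the bleeding condition, the false-success rate is 7.4% to 9.8% if one hsCRP test counts. If any of the four hsCRP comparisons counts, it is about 10% to 14% (biomarker tests at 2.5% favourable) or 15% to 23% (at 5%). The four-test ranges rest on assumed correlations of 0.8 to 0 and on MoCA being uncorrelated with hsCRP; moderate correlation with MoCA changes them little. The rate is higher only if exploratory markers also count, which the rule leaves open.

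Separately, and without any error figure: hsCRP can decide success, section 6.11 makes it available to the Steering Committee at interim, and section 12.3 has that committee approve protocol modifications. In an open-label trial this is a possible source of operational bias. It is a minor matter and does not add to the rates above.

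**What to change.** In the Study Success entry of section 1.1, make the 90-day MoCA test the sole efficacy criterion, keep the bleeding condition, and describe biomarkers as supportive. If a formal biomarker claim is wanted, name one hsCRP comparison (fluid, summary and time points) and test it in fixed sequence, only after a significant MoCA result. Both options keep MoCA at one-sided 5% and its stated 80% power at 40 per arm.

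If the OR is to be kept, name one hsCRP test, split alpha 0.025/0.025, and state in section 10.4 that success is judged at those levels. MoCA power then falls to about 71% at 40 per arm and must be restated, or the sample size raised.

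In section 6.11, limit any interim hsCRP summary by group to the DSMB.

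The first two options and the access change need wording only. The price is losing the biomarker-only route to a success claim; a biomarker reduction without a MoCA benefit can still be reported, as supportive evidence.
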